#### 4.11.5 Vital Signs

Vital signs will be assessed as shown in the Schedule of Assessments (Appendix 6.1). The following vital signs measurements will be obtained:

- Systolic blood pressure (SBP) [mmHg].
- Diastolic blood pressure (DBP) [mmHg].
- Pulse rate (bpm).
- Blood oxygen saturation (SpO2) [%]
- Body temperature [ $^{\circ}\text{C}$ ].

Severity grading for vital signs will be derived according to the [Table 4](#) below.

**Table 4 Vital Signs Severity Grading**

Parameter	Severity Grade		
	Mild	Moderate	Severe
SBP	$139 < x \leq 159$	$159 < x \leq 179$	$x > 179$
DBP	$90 < x \leq 99$	$99 < x \leq 109$	$x > 109$
Pulse rate	$49 < x \leq 55$ or $100 < x \leq 115$	$40 < x \leq 49$ or $115 < x \leq 130$	$x \leq 40$ or $x > 130$
	$93 < x \leq 96$	$91 < x \leq 93$	$x \leq 91$
Body temperature	$35.0 < x \leq 35.9$ or $37.5 < x \leq 38.0$	$38.0 < x \leq 39.0$	$x \leq 35$ or $x > 39.0$

If more than one assessment is performed for a time point, then for summaries the most severe grade will be used.

The following summaries will be provided for each vital sign parameter:

- Results and change from baseline will be summarized descriptively by timepoint and treatment group;
- Number and percentage of subjects will be tabulated by severity grade, visit and overall, for each treatment group;
- Shift from baseline severity grade will be presented by visit and overall, for each treatment group;

By-subject listing of vital signs results with change from baseline and severity grade will be provided by subject, vital sign parameter and timepoint for each treatment group.

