6.4. Inclusion criteria

A subject must meet all of the following criteria to be eligible to participate in this study:

1. Provides written informed consent prior to initiation of any study procedures.
2. Be able to understand and agrees to comply with planned study procedures and be available for all study visits.
3. Agrees to the collection of venous blood per protocol.
4. Confirms to have not donated blood three months before the study
5. Agrees to refrain from blood during the study and until the three months after the end of the study.
6. Body Mass Index 18-29 kg/m², inclusive, at screening.
7. Premenopausal women must agree to use one acceptable primary form of contraception.
8. Premenopausal women must have a negative urine pregnancy test the day of vaccination and are routinely using - and willing to use up to six months from vaccine administration - an effective method of birth control resulting in a low failure rate (i.e., hormonal contraception, condoms in combination with a spermicidal cream, male partner sterilization-vasectomy or total sexual abstinence).
9. Oral temperature ≤37.0 degrees Celsius the day of the administration of the vaccine
10. Pulse no greater than 100 beats per minute.
11. Systolic blood pressure (BP) is 85 to 139 mmHg, inclusive the day of vaccination.
12. Should not show laboratory values outside the normal range which may have clinical significance even in absence of specific signs or symptoms.

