- B. Dose 1×10^{11} vp (arm 2 and arm 5)
- C. Dose 2×10^{11} vp (arm 3 and arm 6)

The injection site will be covered with a sterile dressing and the participants will stay in observation per 4 hours, in case of immediate adverse events. Investigator will decide whether the participant can leave or need additional time in hospital monitoring.

All participants will be vaccinated with the same procedure and according to the same schedule of clinical record. A standard electronic case report forms (e-CRF) will be produced and filled in.

7.2. *Medical visit*

Medical visit will be carried out at the endpoints indicated in the schedule of procedures and will always include a check of medical history, physical examination, weight and height (at screening only), pulse, blood pressure, after 10 min rest in sitting position, and body temperature.

7.3. *Blood test and other analysis for monitoring safety*

Biological testing for monitoring safety will be carried out at the endpoints indicated in the schedule of procedures at the laboratory of the clinical centers that enroll volunteers and will include:

- A. Full Blood Count
- B. Urine analysis
- C. Biochemistry: Sodium, Potassium, , , Albumin, Liver Function Tests (ALT, ALP, Bilirubin total and fractionated), Renal function (Creatinine and BUN), lactate dehydrogenases (LDH), alkaline phosphatases (ALP)
- D. Diagnostic serology: HBsAg, HCV antibodies, HIV antibodies (specific consent will be gained prior to testing blood for these blood-borne viruses)
- E. Coagulation: aPTT (ratio), PT (ratio) and INR.

Urine will be tested for pH, Glucose Protein, Haemoglobin, Leukocyte esterase, Ketones, Bilirubin, Urobilinogen and Nitrites at screening. For female participants only, urine will be tested for beta-human chorionic gonadotrophin (β -HCG) at screening.

Participants presenting with respiratory symptoms consistent with COVID-19 infection will undergo to molecular test for SARS-CoV-2 and admitted to hospital in isolation room until a negative is available.

Additional safety blood tests may be performed if clinically relevant at the discretion of the medically qualified investigators.

Item	Time of the visit since vaccination									Type of intervention
	Scr	T0	D2	W1	W2	W4	W8	W12	W24	
Window (days)	≤ 21	0	0	±1	±1	±2	±4	±7	±14	
Informed consent	x									Procedures
Eligibility	x									
Vaccination		x								
AE reporting		x	x	x	x	x	x	x	x	
Diary card		A				B				
Medical history	x									

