9.7. Management of participants with AE

The clinical center that enroll participants will provide care to any participant with any AE as appropriate for the clinical conditions.

Each enrolling center will have a medical investigator that will ensure real-time safety oversight. The local medical investigator will review AEs deemed possibly, probably or definitely related to study interventions. The local investigator will immediately register AE and will notify them to principal investigator according to SOP. Moreover the local investigator can decide to place the study on hold if deemed necessary following a study intervention-related as severe or unexpected event such as: SAE, UAR, SAR and SUSAR. The decision to put the study on hold is immediately notified to principal investigator and to DSMB.

Table 1 Adverse event severity scale

Adverse events	Severity			
	None	Mild	Moderate	Severe
Erythema	no	3-50 mm	51-100 mm	>100 mm
Swelling	no	3-20 mm	21-50 mm	> 50 mm
Ulceration	-	-	-	any
Fever	36.0-37.4	37.5-38.0	38.1-39.0	>39.0
hypothermia		35.9-35.1	-	<35
Tachycardia (bpm)	55-100	101-115	116-130	>130
bradycardia (bpm)		50-54	40-49	≤40
Systolic hypertension	85-140	141-159	160-179	>179
Systolic hypertension		85-89	80-84	<80
Diastolic hypertension	<90	91-99	100-109	>109
Respiratory Rate low	12-20	-	9-11	<9
Respiratory Rate high		-	21-24	>24
SpO2 at FiO2 21%	>97	94-96	92-93	<92
Consciousness	Alert	-	-	any
Biochemistry	MedDra and CTAE. Grade 1-2=mild; Grade 3/4= severe/life threatening			
Blood counts				

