## 3.2 Endpoints and Associated Variables

### 3.2.1 Safety Variables

- Adverse event (AE) assessments
- Clinical laboratory tests (hematology and clinical chemistry)
- Vital signs (supine blood pressure and pulse, body temperature, respiratory rate and SpO2)
- 12-lead electrocardiograms (ECG): Interpretation
- Physical examinations
- Concomitant medication assessments
- Subject Diary

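### SAP Table 4 has no low-side systolic band, so readings below 85 mmHg, which the protocol grades moderate or severe, get no grade in the by-grade and shift tables

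*SAP*

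**What the plan says.** SAP 4.11.5 makes Table 4 the source of the grades: "Severity grading for vital signs will be derived according to the" table that follows. The systolic row of that table reads "SBP $139 < x \leq 159$ $159 < x \leq 179$ $x > 179". It has no lower band. In the same table, pulse is graded down to 40 bpm and below, and temperature down to 35 °C and below.

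Two outputs rest on these grades: "Number and percentage of subjects will be tabulated by severity grade, visit and overall, for each treatment group", and "Shift from baseline severity grade will be presented by visit and overall, for each treatment group". A third summary (results and change from baseline) and the by-subject listing use the measured values.

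Protocol 9.6 has adverse event severity judged on the scale in protocol Table 1 (section 9.7). Its first systolic row is "Systolic hypertension 85-140 141-159 160-179 >179". A second row carries the same label but grades 85-89 as mild, 80-84 as moderate and below 80 as severe, which can only describe low pressure. Entry under protocol 6.4 requires: "Systolic blood pressure (BP) is 85 to 139 mmHg, inclusive the day of vaccination".

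On posture, protocol 7.2 specifies "pulse, blood pressure, after 10 min rest in sitting position, and body temperature". SAP 3.2.1 lists "Vital signs (supine blood pressure and pulse, body temperature, respiratory rate and SpO2" among the safety variables.

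**The concern.** The trial is first-in-human. It enrols people aged 65-85, and exclusion criterion 13 lets in participants on sartans or ACE inhibitors with a good response. Protocol 15.1.2 names anaphylaxis and immune-mediated reactions as possible risks. A graded vital-sign table is there to count affected participants by severity, arm and visit.

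For low systolic pressure the SAP tables cannot do that. Eligible participants have an SBP of 85-139 on the day of vaccination, so none has a systolic grade at baseline under Table 4. A fall to 75 mmHg, severe under the protocol, would move from ungraded to ungraded and show no shift. Diastolic pressure would not fill the gap, because it is graded only on the high side in both documents.

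A site grading by protocol Table 1 and the SAP derivation could therefore give different answers for the same reading.

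**Working it through.** There is no sample size, power or alpha figure to reproduce. The check grades each possible reading under both tables: every integer for SBP (60-220), diastolic pressure (40-130), pulse (30-150) and SpO2 (80-100), and every 0.1 °C from 34.0 to 41.0. The readings below are those where the tables disagree, or where the protocol gives two grades or none.

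| Reading | Protocol Table 1 | SAP Table 4 |
|---|---|---|
| SBP below 80 | Severe | no grade |
| SBP 80-84 | Moderate | no grade |
| SBP 85-89 | None and Mild | no grade |
| SBP 140 | None | Mild |
| Pulse 40 | Moderate and Severe | Severe |
| Pulse 55 | None | Mild |
| Temperature 35.0 | no grade | Severe |
| Temperature 37.5 | Mild | no grade |
| Diastolic 90 | no grade | no grade |
| SpO2 97 | no grade | no grade |

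1. **Systolic.** From 60 to 220 mmHg the mismatches are 20 values (60-79) + 5 (80-84) + 5 (85-89) + 1 (140) = 31. These are possible values, not expected readings, and the 20 depends on where the grid starts.
2. **The clean conflict.** Below 85 mmHg the protocol gives one grade and the SAP gives none, so the moderate and severe bands are lost. At 85-89 the protocol gives both None (85-140) and Mild (85-89), and entry is allowed from 85. The SAP cannot be said to contradict a single protocol grade there.
3. **Other parameters.** Diastolic pressure and SpO2 agree wherever the protocol gives a grade. Pulse and temperature differ only at single boundary values. Protocol 7.8 also uses 37.5 °C as an inclusive limit.
4. **Respiratory rate.** It is graded in protocol Table 1 and listed in SAP 3.2.1. It is absent from protocol 7.2, from SAP 4.11.5 and Table 4, and from both schedules (protocol Figure 9, SAP Table 5).
5. **What one case would change.** With 15 participants per arm, one participant with an SBP below 80 mmHg at a visit should make the severe count 1/15 = 6.7%. Under Table 4 it stays at 0/15. The documents give no expected rate of such readings, so the number affected cannot be estimated.

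**The case against.** The strongest reply is that little is hidden. SAP 4.2 requires the minimum and maximum, and the text after Table 4 requires change from baseline and a listing. With 15 per arm, a 75 mmHg reading would stand out as an arm-visit minimum. Hypotension reported as an adverse event would be graded on the protocol scale and, if it began within 28 days, would enter the treatment-emergent summaries by maximum severity (SAP 4.11.1). The halting rules in protocol 9.8 use adverse event severity, seriousness and relatedness, not derived vital-sign grades. All of this stands and limits the point to two outputs. It does not remove it: a minimum does not count participants by grade and arm.

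Four stronger readings are tempting, and the documents do not support them:

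- **A low SBP is tabulated as normal.** Table 4 defines no normal category. The reading simply has no grade.
- **Every reading below 90 mmHg loses a protocol grade.** At 85-89 the protocol itself gives two answers.
- **An acute reaction after injection would be missed.** Time 0 vital signs are taken before vaccination (protocol 7.6), and neither schedule lists a reading during the 4-hour observation. An acute fall would surface mainly as an adverse event or an unscheduled reading. The scheduled by-visit tables are affected from day 2 onward.
- **Dose escalation is compromised.** SAP 4.11.7 says the monitoring board's outputs follow the SAP as appropriate, with separate shells. The gap could carry over, but nothing shows that it does.

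The supplied protocol may also not be the text that the SAP implements. SAP 1 cites Version 2.0. SAP 4.11.3 places the safety blood tests in protocol section 8.3, but here they are in 7.3. The screening window is 28 days in the body of SAP Table 5 and 21 in protocol Figure 9. Some cut differences could come from this. It would not explain why Table 4 grades both tails of pulse and temperature but one tail of SBP, although diastolic pressure is one-sided too, so intent cannot be proved.

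**Conclusion.** The point holds within narrow limits. SAP Table 4 cannot register low systolic pressure, and two protocol grades (80-84 moderate, below 80 severe) have no counterpart in the by-grade and shift tables. Descriptive summaries, listings and adverse event reporting are unaffected.

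The boundary values, posture and respiratory rate are minor alignment points. They add nothing to the weight of the systolic gap.

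This should be corrected before the graded tables are relied on, but it does not put the safety analysis as a whole in doubt. The conclusion assumes that the second systolic row of protocol Table 1 is meant for low pressure, as its values show, and that the protocol version behind the SAP has a similar row.

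**What to change.** 1. In the protocol version that the SAP implements, reconcile Table 1: correct the label of the second systolic row, and resolve the 85-89 overlap with the None band in the light of the entry range.
2. Carry the reconciled low-side systolic grades into SAP Table 4.
3. Reconcile the boundary values (SBP 140, pulse 40 and 55, temperature 35.0 and 37.5) so that each has one grade in both documents.
4. Reconcile the posture in protocol 7.2 with that in SAP 3.2.1, and state what was actually done.
5. Reconcile the respiratory-rate passages so that the variable lists, the grading tables and the schedules agree on whether it is collected.
6. Rerun the by-grade and shift tables, and check whether the monitoring board's shells use the same derivation.

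This review does not say which thresholds or posture are right.

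The cost is one SAP table edit, one reprogrammed derivation and a wording correction in the protocol. A few more readings will be graded. The systolic, pulse and temperature changes use data already collected. Respiratory rate would need new collection only if it is kept as a scheduled measurement.

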#### 4.11.6 Physical Examination

Physical examinations will be performed as shown in the SoA. By subject listing using SAF will be provided for overall results and body system with abnormal observation. Listing will be provided by subject and timepoint for each treatment group.

#### 4.11.7 Safety Monitoring (Data and Safety Monitoring Board [DSMB])

The main roles of the DSMB for this study will be:

- decision-making on dose escalation, escalation intervals and cohort extension (if applicable).
- Monitoring all safety data recorded while the study is on-going.
- Proposing changes in the design and operations of the trial during the course of the study. For documented safety reasons, the DSMB can suggest and discuss with the Sponsor the interruption of the study. In case this decision will be agreed, the Sponsor should ensure the interruption in a reasonable timeframe, complying with ICH-GCP and all applicable Regulations.

The justification for the establishment of the DSMB and the grounds for dose escalation, as well as the DSMB procedures is provided in the DSMB charter.

Seven DSMB meetings are planned prospectively, in order to:

- DSMB authorizes ARM1 group B and ARM2 Group A
- DSMB authorizes ARM2 group B and ARM3 Group A
- DSMB authorizes ARM3 group B
- DSMB revises 4-week safety of whole Arm-1. DSMB authorize enrollment in ARM4 Group A.
- DSMB authorizes ARM4 Group B and ARM5 Group A
- DSMB authorize ARM5 Group B and ARM6 Group A
- DSMB authorize ARM6 Group B

Tables, listings, and figures (TLFs) provided for the DSMB are created by the Parexel statistical team. All TLFs (planned and ad-hoc) created for the DSMB are developed following the guidelines defined in this SAP, as appropriate. Specifications for these outputs are included in a separate TLF shells dedicated to solely supports the review conducted by the DSMB.

## 4.12 Other Analyses

### 4.12.1 Subject Diary Data

Diary data summaries will be based upon the SAF as defined in Section 4.5. Summaries will be grouped by treatment as indicated in [IA: Interim analysis. FA: Final analysis.](#)

#### [1] AE and Categorical Safety only

[Table 3](#) at Section 4.2.

Subject are provided with diary cards as indicated in Schedule of Assessments (Appendix 6.1) and instructed to record systemic and injection site adverse event in diary for four weeks post vaccination. Daily source data are entered in the respective Diary eCRFs.

Summary on severity will be provided over all systemic adverse events (Nausea, Vomiting, Diarrhea, Abdominal Pain, Headache, Muscular Pain, Fatigue and Chills), injection site pain and ulcer by treatment groups, days and weeks. By time point severity over all systemic adverse events will be calculated by counting the number of subjects in each severity categories in any AE term.

By-subject listings of diary data will include records with any severity as well as swelling, redness, ulceration and body temperature daily assessments.

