7.8. Visit (D2, W1, W2, W4, W8, W12 and W24)

Follow-up visits will take place 48h after the vaccination (D2) and eventually at week 1 (W1), 2 (W2), 4 (W4), 8 (W8), 12 (W12), 24 (W24) and 48 (W48) after vaccination. Participants will be assessed for local and systemic AE, interim history, physical examination, review and blood tests at these endpoints. Blood will also be taken for exploratory immunology purposes.

If a participant experience adverse events (laboratory or clinical), which the investigator (physician) determine necessary for further close observation, the participant may be admitted to the clinical facility of the enrolling center. Moreover, investigator can decide to perform additional medical examination if needed.

Participants who experience symptoms that are associated with COVID-19 including fever ≥ 37.5 °C and/or respiratory symptoms will be treated according to local guideline for suspect cases of COVID-19 until an infection with SARS-CoV-2 is not excluded by a molecular test. A test for detection of SARS-CoV-2 on respiratory sample will be carried out on all participants with fever ≥ 37.5 °C persisting for more than 48 hours at any time after vaccination. Participants with confirmed COVID-19 will be admitted to hospital until clearance of the infection.

Schedule of attendance is reported in Figure 9.

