Suspect unexpected serious adverse reaction (SUSAR). A severe adverse reaction, the nature and severity of which is not consistent with the information about the medicinal product in question set out in the investigator brochure (IB) or Summary of Product Characteristics.

9.2. *Solicited Adverse Reactions*

Solicited Adverse Reactions are those (foreseeable) AEs following vaccination with GRAd-COV2, and include injection site pain, erythema, warmth, swelling, pruritus, myalgia, arthralgia, headache, fatigue, fever, feverishness, malaise and nausea.

Solicited Adverse Reactions are grade as following:

- A. None: Symptom does not experience
- B. Mild: Short-lived or mild symptoms; medication may be required. No limitation to usual activity
- C. Moderate: Mild to moderate limitation in usual activity. Medication may be required but hospitalization is not required.
- D. Severe: Considerable limitation in activity. Invasive intervention or hospitalization is required.

We do not expect life threatening or fatal solicited adverse reactions in this study.

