9.8. Halting rules and study termination due to safety issue

Safety halting rules have been developed considering the fact that this is a *first-in-human* dose escalation study. Solicited adverse events are those listed as in section 9.2, occurring within the first 7 days after vaccination (day of vaccination and six subsequent days). Unsolicited adverse events are AE other than the solicited AEs occurring within the first 7 days, or any AEs occurring after the first 7 days after vaccination.

Enrolment of participants in one arm will be upheld if:

- A. Solicited local adverse events (site of injection): 2 or more vaccinations in a group are followed by the same severe solicited local adverse event beginning within 2 days after vaccination (day of

vaccination and one subsequent day) and persisting at severe for >48 hrs and these are deemed possibly, probably or definitely related to study interventions.

- B. Solicited systemic adverse events: If 2 or more vaccinations in a group are followed by the same severe solicited systemic adverse event beginning within 2 days after vaccination (day of vaccination and one subsequent day) and these are deemed possibly, probably or definitely related to study interventions.
- C. Unsolicited adverse events: If 2 or more vaccinations in a group are followed by the same serious unsolicited adverse event (including the same laboratory adverse event) and relation with vaccination cannot be immediately excluded.
- D. One participant with serious adverse event considered possibly, probably or definitely related to vaccination occurs
- E. Life-threatening condition when relation with study intervention cannot be immediately excluded.
- F. Death when relation with study intervention cannot be immediately excluded.

If a halting rule has been met, we will inform the regulatory authority. Moreover, before restarting enrollment the DSMB should exclude that AE has no immediate causal relation with the vaccine or that benefit of vaccination outweigh risk of further AE occurrence. In these latter case Ethical committee should be involved in the decision. Halting rules apply to one dose and the next higher one, so that if halting rule is met for the highest dose, only this arm is upheld. If halting is met for intermediate dose, two arms are held. If halting rule is met for the lowest dose all the study is stopped pending on the investigation of causal association between AE and vaccination (DSMB advice).

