15.1.1. Phlebotomy

The maximum volume of blood drawn over the study period (approximately 465 mL) should not compromise these otherwise healthy volunteers. There may be minor bruising, local tenderness or pre-syncopal symptoms associated with venopuncture, which will not be documented as AEs if they occur.

15.1.2. Vaccination:

GRAd-COV2 has not been used in humans before and therefore will be initially administered at the lower dose of 5×10^{10} vp before progressing to the higher doses of 1×10^{11} and 2×10^{11} in the arms 2,3 ,5 and 6. Potential expected risks from vaccination include local effects such as pain, redness, warmth, swelling, tenderness or itching. Systemic reactions that could potentially occur following immunization with a recombinant adenovirus vaccine include a flu-like illness with feverishness, fatigue, malaise, arthralgia, myalgia and headache.

As with any vaccine, Guillain-Barré syndrome or immune-mediated reactions that can lead to organ damage may occur, but this should be extremely rare. Serious allergic reactions including anaphylaxis could also occur and for this reason volunteers will be vaccinated in a clinical area where Advanced Life Support trained physicians, equipment and drugs are immediately available for the management of any serious adverse reactions (SAR).

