#### 4.11.1 Adverse Events

Adverse events (AEs) will be coded using the Medical Dictionary for Regulatory Activities (MedDRA) Version 23.0.

An AE is any untoward medical occurrence in a study subject administered an IMP which does not necessarily have a causal relationship with this treatment. An AE can therefore be any unfavorable and unintended sign (including a clinically significant abnormal laboratory finding), symptom, or disease temporally associated with the use of an IMP, whether or not considered related to the IMP. Adverse events may include the onset of new illness and the exacerbation of pre-existing conditions.

Other untoward events occurring in the framework of a clinical study will be recorded as AEs, e.g. those occurring during treatment-free periods (including Screening or post-treatment Follow-up periods), in association with study-related procedures and assessments or under placebo.

Concomitant illnesses, which existed before entry into the clinical study, will not be considered AEs unless they worsen during the treatment period. Pre-existing conditions will be recorded as part of the subject's medical history.

A treatment-emergent adverse event (TEAE) is defined as an AE that begins or worsens in severity in 28 days after study drug administration.

Adverse event with 'No Relationship' or 'Unlikely Related' causality will be evaluated as not related (relationship = No), otherwise (including missing causality) AE will be evaluated as related (relationship = Yes).

Adverse events with completely unknown start dates will be considered as treatment-emergent for the tabulations and will be shown as NK in the listings. Partially complete AE dates will not be imputed in the listings and the available day, month and year components will be used to determine if an adverse event is treatment-emergent taking the first dosing date and end of study date as references.

Solicited adverse reactions are foreseeable AEs following vaccination with GRAd-COV2 including the following AEs: injection site pain, erythema, warmth, swelling, pruritus, myalgia, arthralgia, headache, fatigue, fever, feverishness, malaise and nausea. Solicited adverse reaction is recorded as such on the corresponding AE's eCRF.

Adverse events of special interest (AESI) are any grade  $\geq 3$  abnormalities on safety blood test according to Common Terminology Criteria for Adverse Events v.5.0 (CTCAE, see section [4.11.3](#)).

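### The diary items named in SAP 4.12.1 do not match the solicited list: 5 of 13 solicited reactions have no named diary item, and 5 diary items are off the list

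*SAP*

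**What the plan says.** Protocol 9.2 defines the solicited reactions as "injection site pain, erythema, warmth, swelling, pruritus, myalgia, arthralgia, headache, fatigue, fever, feverishness, malaise and nausea", which is 13 terms. SAP 4.11.1 repeats the same 13. Primary endpoints A and B (Protocol 4.2.1) are the solicited local and systemic events over 7 days, and endpoint C is unsolicited events over 28 days.

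SAP 4.12.1 describes the diary. Subjects are "instructed to record systemic and injection site adverse event in diary for four weeks post vaccination". The severity summary covers all "systemic adverse events (Nausea, Vomiting, Diarrhea, Abdominal Pain, Headache, Muscular Pain, Fatigue and Chills), injection site pain and ulcer". By-subject listings also include "swelling, redness, ulceration and body temperature daily assessments". No other diary item is named, and neither document reproduces the card.

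Protocol 9.8 identifies solicited events by reference to the 9.2 list and then states: "Unsolicited adverse events are AE other than the solicited AEs occurring within the first 7 days"; anything after 7 days is also unsolicited. Halting rules A and B in that section apply to solicited local and solicited systemic events.

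Two further routes of capture are described. Protocol 7.8 says of the follow-up visits: "Participants will be assessed for local and systemic AE, interim history, physical examination". SAP 4.11.1 says: "Solicited adverse reaction is recorded as such on the corresponding" AE eCRF page, and plans one summary of solicited reactions in the first 7 days by system organ class and preferred term.

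**The concern.** A solicited reaction is one that every subject is asked about in the same way, on the same days. That is what makes its rate comparable between arms and between terms. If some listed terms have a daily diary item and others do not, one solicited table mixes systematic and opportunistic ascertainment. A low rate of arthralgia or malaise could then mean that the reaction was rare or that it was not recorded, and the table would not show which.

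The mismatch also runs the other way. A symptom recorded daily in the diary but missing from the list becomes unsolicited by definition, although it was gathered in the same way as headache or fatigue. The trial is descriptive with 15 subjects per arm, so how events are ascertained bears directly on the primary safety rates. Because 9.8 uses the same list for halting rules A and B, the mismatch reaches those rules too.

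**Working it through.** No alpha, power or sample-size figure enters, and the plan states no figure to reproduce. The check is a comparison of two lists.

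**Inputs.** Solicited list: 13 terms (Protocol 9.2, SAP 4.11.1). Diary items (SAP 4.12.1): 8 systemic + injection site pain + ulcer = 10 in the severity summary. The listings add swelling, redness and body temperature (ulceration repeats ulcer), so 10 + 3 = 13 distinct items. That both totals are 13 is a coincidence.

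**Step 1: solicited terms against diary items.** Synonyms mapped: muscular pain = myalgia, redness = erythema, body temperature = fever.

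| Solicited term | Named diary item | Planned diary output |
|---|---|---|
| Injection site pain | yes | severity summary |
| Erythema | redness | listing only |
| Warmth | none | – |
| Swelling | yes | listing only |
| Pruritus | none | – |
| Myalgia | muscular pain | severity summary |
| Arthralgia | none | – |
| Headache | yes | severity summary |
| Fatigue | yes | severity summary |
| Fever | body temperature | listing only |
| Feverishness | none | – |
| Malaise | none | – |
| Nausea | yes | severity summary |

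Matched: 8. Unmatched: 13 − 8 = 5, and 5/13 = 38%.

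**Step 2: diary items not on the solicited list.** Vomiting, diarrhea, abdominal pain, chills and ulcer: 13 − 8 = 5, of which four are systemic and one local.

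**Step 3: sensitivity to the mapping.**

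| Reading | Solicited terms without an item | Diary items off the list |
|---|---|---|
| Strict match | 5 of 13 (38%) | 5 |
| Body temperature also covers feverishness | 4 of 13 (31%) | 5 |
| Chills taken as feverishness | 4 of 13 (31%) | 4 |
| Only the 10 items in the severity summary | 8 of 13 (62%) | 5 |

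**Step 4: the protocol's own expectation.** Protocol 15.1.2 anticipates a "flu-like illness with feverishness, fatigue, malaise, arthralgia, myalgia and headache": six systemic reactions. Three of them (feverishness, malaise, arthralgia) have no named diary item, or two if feverishness is treated as covered.

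**Step 5: timing of the other route.** The solicited window in 9.8 is the vaccination day plus the six days after it. The follow-up visits nearest to it are D2 and W1. W1 has a ±1 day window, so it falls 6 to 8 days after vaccination, at or after the end of the solicited window. Questions put there rely largely on recall, whereas a matched term has an entry for each day.

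**Step 6: what one missed subject is worth.** In an arm of 15, each unrecorded case lowers the observed rate by 1/15 = 6.7 percentage points; in a cohort of 45, by 1/45 = 2.2 points. The number of such cases cannot be derived from the documents.

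**Step 7: diary tables.** The SAP pools severity across all systemic terms at each time point. It plans no incidence by individual diary term, so the planned outputs would not let a reader compare ascertainment of matched and unmatched terms.

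**The case against.** The strongest reply is that SAP 4.12.1 specifies outputs, not the questionnaire. The card is not shown, the instruction to subjects is general, investigators assess adverse events at visits, and the solicited table is built from the AE eCRF flag over all 13 terms, not from the diary. A reader might infer that the five terms were never asked about, or that endpoints A and B are shown to be biased. The documents support neither inference.

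What remains is this. The SAP describes its bracketed list as covering all systemic events and then adds four listing items. Either the card holds no item for the missing terms, or it does and the planned outputs leave out collected solicited data. Both need correcting. No text says that the 9.2 terms are put to subjects one by one at visits, and no rule says how a diary entry reaches the AE eCRF.

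A reader might also infer that endpoint C is inflated by diary-recorded reactogenicity. The SAP plans no separate unsolicited table, and classification in the data depends on the eCRF flag, so this is conditional. Counting only four diary items as off the list is also incomplete: it leaves out ulcer.

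Finally, one might conclude that severe off-list events escape the halting rules. That goes too far. Rules C to F in 9.8 cover serious unsolicited events, a single related serious event, life-threatening conditions and death. The severe grade in 9.2 refers to invasive intervention or hospitalization, and 9.1 makes any hospitalization serious. Local investigators may also place the study on hold (9.7). The gap is confined to off-list events that are severe but not serious. Ulceration is the clearest example: Table 1 in Protocol 9.7 grades any ulceration as severe, yet it is not a solicited local event for rule A.

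**Conclusion.** The mismatch is real, and neither document reconciles it. Five of 13 solicited reactions have no named diary item (four under the wider reading of feverishness), and five diary items are off the list (four if chills is taken as feverishness). Terms in the single 7-day solicited table would be ascertained unequally, and rates of warmth, pruritus, arthralgia, feverishness and malaise may be understated. The size of any understatement cannot be estimated from the documents.

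This rests on two assumptions: that SAP 4.12.1 names all the diary items, and that the synonyms in Step 1 are accepted. It does not establish that the five terms went uncollected, that any endpoint is biased by a given amount, or that an unsolicited count is inflated. It does limit what the solicited table for endpoints A and B can support, and it should be corrected.

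**What to change.** 1. **Future diaries.** Add warmth, pruritus, arthralgia, feverishness and malaise to the card.
2. **Diaries already completed.** State in SAP 4.11.1 and 4.12.1 which solicited terms had a daily diary item, and how diary entries map to AE eCRF terms and to the solicited flag.
3. **Solicited table.** Keep the protocol's 13-term, 7-day table as the pre-specified one. Alongside it, show the terms without a diary item separately, labelled as not systematically solicited.
4. **Diary table.** Add a 7-day incidence table by individual term for every diary-recorded item, including vomiting, diarrhea, abdominal pain, chills, ulcer, swelling, redness and temperature.
5. **Endpoint C.** In any unsolicited summary, identify diary-recorded events separately.
6. **Halting rules.** Protocol 9.2, Table 1 in 9.7, 9.8 and SAP 4.12.1 must be reconciled by the sponsor and the DSMB. Adding terms to 9.2 would change what rules A and B cover, so it should not be done as a tabulation fix. No halting rule is proposed here.

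The cost is a few more diary items for future subjects, some SAP text and one or two extra tables. No data already collected need to be discarded, and the pre-specified analysis is unchanged.
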